12.3.6. Interim Analysis

No interim analysis is planned in this study.

13. INSTITUTIONAL REVIEW BOARD APPROVAL

The study proposal will be submitted to the Institutional Review Board (IRB) in accordance with US requirements.

The IRB shall give its opinion in writing -clearly identifying the study number, study title and informed consent form approved-, before the clinical trial commences.

A copy of all communications with the IRB will be provided to the Sponsor.

The Investigator should provide written reports to the IRB annually or more frequently if requested on any changes significantly affecting the conduct of the trial and/or increasing risk to the subjects (according to the requirements of each country).

14. REGULATORY REQUIREMENTS

The study will be notified to the Health Authorities (or authorized by) according to the legal requirements in the US. In the case of a substantial amendment, approval from the Health Authority will be sought before implementation.

Selection of the subjects will not start before the approval of the IRB has been obtained and the study notified to Health Authorities (or authorized by).

The study will be conducted in accordance with the Declaration of Helsinki, with the Good Clinical Practices guidelines and following all other requirements of local laws.

15. INFORMED CONSENT

It is the responsibility of the Investigator to obtain written consent from each subject's parent or the parents' legal representative prior to any study related procedures taking place, by using the latest IRB approved version of the Informed Consent document.

If the subject's parents or the parents' legal representative are unable to read, the informed consent will be obtained in the presence of an impartial witness, e.g. a person independent of the study who will read the informed consent form and the written information for the parents.

Adequate time shall be given to the subjects' parents or legal representative to ask the PI about any clarifications needed and to consider parents' decision to enroll the subject in the study.

Consent must be documented by the dated signature. The signature confirms that the consent is based on information that has been understood. Moreover, the Investigator must sign and date the informed consent form.

Each signed informed consent must be kept on file by the Investigator. One copy must be given to the subject.

16. SOURCE DOCUMENTS/DATA

16.1. Recording of source data

Data collection is the responsibility of the clinical trial staff at the site under the supervision of the site investigator. The investigator is responsible for ensuring the accuracy, completeness, legibility, and timeliness of the data reported. All source documents should be completed in a neat, legible manner to ensure accurate interpretation of data.

Data recorded in the eCRF derived from source documents should be consistent with the data recorded on the source documents ([APPENDIX II](#)).

16.2. Direct access to source document/data

The Investigators or designated must permit trial-related monitoring, audits, IRB review or regulatory inspection, providing direct access to source data/documents.

17. STUDY MONITORING

Monitoring will be performed by the CRO, [REDACTED], who has been designated by Chiesi Farmaceutici S.p.A.

It is understood that the monitor(s) will contact and visit the Investigator/center before the study, regularly throughout the study and after the study had been completed, and that they will be permitted to inspect the various study records: case reports form, Investigator study file and source data, provided that subject confidentiality is respected.

The purposes of these visits are:

- to assess the progress of the study;
- to review the compliance with the study protocol;
- to discuss any emergent problem;
- to check the eCRFs for accuracy and completeness;
- to validate the contents of the CRFs against the source documents;
- to assess the status of drug storage, dispensing and retrieval.

Prior to each monitoring visit, the Investigator or staff will record all data generated since the last visit on the eCRF. The Investigator and/or study staff will be expected to be available for at least a portion of the monitoring visit to answer questions and to provide any missing information.

It is possible that the Investigator site may be audited by Sponsor personnel or regulatory national and/or international regulatory agencies during and after the study has been completed.

18. QUALITY ASSURANCE

The R&D Quality Assurance Department of Chiesi Farmaceutici S.p.A may perform an audit at any time according to the Sponsor's Standard Operating Procedures, in order to verify whether the study is being conducted in agreement with Good Clinical Practices and protocol.

19. INSURANCE AND INDEMNITY

Chiesi Farmaceutici S.p.A. holds and will maintain an adequate insurance policy covering damages arising out of Chiesi's sponsored clinical research studies.

Chiesi Farmaceutici S.p.A. will indemnify the Investigator and hold him/her harmless for claims for damages arising out of the investigation, in excess of those covered by his/her own professional liability insurance, providing that the drug was administered under his/her or deputy's supervision and in strict accordance with accepted medical practice and with the study protocol.

The Investigator must notify Chiesi Farmaceutici S.p.A. immediately upon notice of any claims or lawsuits.

20. CONFIDENTIALITY

All study documents are provided by the Sponsor in confidence to the Investigator and his/her appointed staff. None of this material may be disclosed to any party not directly involved in the study without written permission from Chiesi Farmaceutici S.p.A.

The Investigator must assure the subject's anonymity will be maintained. The Investigator will keep a separate list with at least the initials, the subject's study numbers, names, addresses and telephone numbers. The Investigator will maintain this for the longest period of time allowed by his/her own institution and, in any case, until further communication from Chiesi Farmaceutici S.p.A.

21. PREMATURE TERMINATION OF THE STUDY

The Sponsor, Competent Authorities and the Investigator reserve the right to terminate the study at any time. Should this be necessary, the procedures for an early termination or temporary halt will be arranged after consultation by all involved parties.

The Sponsor should submit a written notification to the Regulatory Authority concerned and the IRB providing the justification of premature ending or of the temporary halt.

22. CLINICAL STUDY REPORT

The clinical study report, including the statistical and clinical evaluations, shall be prepared and sent to the Lead Investigator for agreement and signature.

At the end of the trial a summary of the clinical study report will be provided to all IRBs, to the Competent Authority of the US and to the Investigators.

23. RECORD RETENTION

After completion of the study, all documents and data relating to the study will be kept in an orderly manner by the Investigator in a secure study file.

Regulations require that essential documents must be retained for at least two years after the final marketing approval in an ICH region or until two years have elapsed since the formal interruption of the clinical development of the product under study.

It is the responsibility of the Sponsor to inform the Investigator of when these documents can be destroyed. The Investigator must contact Chiesi Farmaceutici S.p.A. before destroying any trial-related documentation. In addition, all subjects' medical records and other source documentation will be kept for the maximum time permitted by the institution.

24. PUBLICATION OF RESULTS

Chiesi Farmaceutici S.p.A. is entitled to publish and/or present any results of this study at scientific meetings, and to submit the clinical trial data to national and international Regulatory Authorities, and if they fall under the Chiesi commitments on Clinical Trial Transparency, to make them available on www.chiesi.com website. Furthermore, Chiesi Farmaceutici S.p.A. reserves the right to use such data for industrial purposes.

In the absence of a Study Steering Committee, Investigators will inform Chiesi Farmaceutici S.p.A. before using the results of the study for publication or presentation and agree to provide the Sponsor with a copy of the proposed presentation. Data from individual study sites must not be published separately.

Negative as well as positive results should be published or otherwise made publicly available.

APPENDIX II**MINIMUM LIST OF SOURCE DATA REQUIRED**

- Date of informed consent signature
- Demographic data
- Study number
- Subject identity/number
- Randomization number
- Complications during pregnancy
- Neonatal comorbidities
- Neonatal Concomitant Medications
- Date of specific study visits
- Labels of study drugs
- Examination or assessments carried out during the study (please refer to [Table 2](#))
- Laboratory reports (blood gas analysis)
- Adverse events / serious adverse events
- 24-month clinical assessment (Bayley scales, health status questionnaire)
- If subject is withdrawn, reason for withdrawal

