3. STUDY DESIGN

This is an open-label, multicenter, randomized and controlled study. Approximately 25 investigational sites will be involved in US. Neonates will be evaluated according to the selection criteria and then randomized to surfactant treatment via LISA or standard administration procedure ([Table 1](#)). The enrollment will be staggered: the gestational age will be restricted to 27⁺⁰ weeks up to 28⁺⁶ completed weeks until safety evaluation by ISMB is performed for the first 15 neonates. Provided no safety concerns are raised, the enrollment will then be extended to the whole population (i.e. 25⁺⁰ weeks up to 28⁺⁶ completed weeks).

[figure not shown]
Enrolled neonates will be evaluated:

- until discharge,
- until 40 weeks PMA (if still in hospital),
- if discharge occurs before 36 weeks, the last evaluation will be at 36 weeks PMA.

This period represents the main phase of the trial.

Their final assessment of development will be at 24-month corrected age as a separate stand-alone visit. This 24-month clinical assessment will be analyzed and evaluated separately from the initial part of the study and will be object of an addendum to the initial core clinical study report.

Table 1: TIMETABLE

End of the trial

The end of the trial will correspond to the last evaluation of the last neonate from the recruiting site or from the continuing care site in case the treated baby was transferred from the original recruiting site. The last evaluation could be:

- the date of the assessment for BPD diagnosis (i.e. 36 weeks PMA) if the patient is discharged home before 36 weeks PMA,
- discharge home (if discharged between 36 weeks and 40 weeks PMA), or
- 40 weeks PMA (if still in hospital).

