7.1.9 Clinical assessment at 24 months (± 3 months) corrected age

A further clinical assessment will be performed at 24 months (± 3 months) corrected age at the participating study centers. In this occasion, age and age corrected for prematurity will be collected. This clinical assessment will be based on:

- Bayley Scales of Infant Development Edition III or IV (see Section [7.2.4](#));
- Health status questionnaire (additional evaluation of growth and development, respiratory assessment);
- Vital signs (SBP, DBP, MBP, HR and RR);
- Body weight, length and OFC.

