To measure cognitive and language development, the score from the related sections of the Bayley Scales III and IV (i.e. cognitive and language domains) will be reported in the questionnaire. Bayley Scales of Infant Development is a standard series of measurements used primarily to assess the motor (fine and gross), language (receptive and expressive), and cognitive development of infants and toddlers, aged 0-3. This measure consists of a series of developmental play tasks and takes between 45 - 60 minutes to administer. Raw scores of successfully completed items are converted to scale scores and to composite scores. These scores (recorded in the eCRF) are used to determine the child's neurodevelopmental performance compared with norms taken from typically developing children of their age (in months).

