11. DATA MANAGEMENT

An electronic case report form (eCRF) to be filled in by the investigator and/or his/her designee will be used. Access to electronic systems used for data collection will be granted to the study personnel only after appropriate training.

Front-end edit checks will run at the time of data collection and back-end edit checks will be run by the CRO Data Manager to check for discrepancies and to ensure consistency and completeness of the data.

Conditions pre-existing to the start of the procedure, concomitant procedures (even if recorded in a different form) and adverse events will be coded using the MedDRA dictionary while medications will be coded using the WHO Drug dictionary and Anatomical Therapeutic Chemical classification (ATC). The same dictionaries will be used to code mother's medical history, complications during pregnancy and mother's prenatal medications.

After cleaning of the data, a review meeting will be held to determine the occurrence of any protocol violation and to define the subject populations for the analysis.

Once the database of the main phase study has been declared to be complete and accurate, the eCRF forms will be locked and the planned statistical analysis will be performed. Only authorized and well-documented updates to the study data are possible after eCRF forms lock.

The Investigators will receive electronic copies of the subject data for retention at the investigational sites.

The 24-month clinical assessment data will be collected and recorded in a separate visit of the database: once all the data of the 24-month clinical assessment has been declared to be complete and accurate, the complete database will be locked and the planned statistical analysis for this assessment will be performed.

The complete database, including the main phase data, will be newly transferred. Comparing procedures documenting anything hasn't been changed in the main phase study data, will be prepared and archived in the TMF.

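### Nothing requires the 24-month examiner to be unaware of the treatment arm, so the descriptive developmental contrast between arms is open to avoidable scoring bias

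*Protocol*

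**What the plan says.** Section 3 of the protocol sets the design: "This is an open-label, multicenter, randomized and controlled study". It makes no exception for any assessment.

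Section 7.1.9 says only where and when the late visit takes place: "A further clinical assessment will be performed at 24 months (± 3 months) corrected age at the participating study centers". It does not say who examines the child, or what that person may know. Appendix II names the visit as an entry in the source-data list, "24-month clinical assessment (Bayley scales, health status questionnaire", and is likewise silent on the examiner.

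Section 7.2.4 describes the Bayley scales: "This measure consists of a series of developmental play tasks and takes between 45 - 60 minutes to administer". The same section lists questionnaire items on cerebral palsy, seizures, vision, hearing, communication and respiratory morbidity. The respiratory part is aimed mainly at the severity of BPD at two years.

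On reporting, Section 3 says that the 24-month assessment "will be analyzed and evaluated separately from the initial part of the study and will be object of an addendum" to the core report. Section 11 provides two locks. The first is for the main phase: "Once the database of the main phase study has been declared to be complete and accurate, the eCRF forms will be locked" and the planned analysis is run. The second follows once the 24-month data are complete. Section 22 provides that investigators, among others, receive a summary of the study report at the end of the trial. Section 3 defines that end as the last main-phase evaluation of the last neonate.

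Section 12.3.5 plans descriptive statistics by arm and Bayley version (III or IV) for the scores, and frequencies or descriptive statistics by arm for the rest.

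**The concern.** Open-label care is unavoidable when the catheter or tube is in view. That reason does not carry over to a developmental examination about two years later, when nothing about the procedure need be visible to the examiner. A site that follows the protocol exactly may still have the child scored by someone who carried out the procedure or has the allocation in front of them.

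There is also a prior expectation. Section 1.2 reports that less invasive methods have been associated with less mechanical ventilation and lower mortality and BPD. Examiners who know the arm, and for some children also the trial's own main-phase results, could lean in one direction without intending to.

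At stake is the reading of the only safety variables that Section 9 lists beyond 40 weeks PMA. Weight, length, head circumference and vital signs at that visit are little affected. The Bayley, cerebral palsy, communication and respiratory items are the exposed ones.

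**Working it through.** **1. What binds the examiner.** Set side by side, Section 3 gives an open-label design without exception, Section 7.1.9 gives place and time, and Section 7.2.4 gives content. None states a rule on masking or on independence from the treating team. Masking of an assessor is a matter of trial conduct, so it belongs in the protocol and is not a detail that a statistical analysis plan would supply.

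**2. Timing.** Inputs: gestational age at birth 25+0 to 28+6 weeks (Section 4.2); visit at 24 ± 3 months corrected age (Section 7.1.9); main-phase evaluation ending at 40 weeks PMA at the latest (Section 3). I count corrected age from 40 weeks PMA and take 4.345 weeks to a month.
- Birth to 40 weeks PMA: 40 − 25 = 15 weeks (3.5 months), or 40 − 28 6/7 = 11.1 weeks (2.6 months).
- Visit after 40 weeks PMA: 24 − 3 = 21 months to 24 + 3 = 27 months.
- Visit after birth: 2.6 + 21 = 23.6 months to 3.5 + 27 = 30.5 months.

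The last child's visit therefore comes 21 to 27 months after that child reaches 40 weeks PMA. This leaves ample time for a main-phase lock, a report and the Section 22 summary.

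For the first child the order depends on the length of recruitment. If R is the time in months from first to last enrolment, the first visit falls before the last child reaches 40 weeks PMA when R exceeds the visit time after birth less 2.6 to 3.5 months. That is from 23.6 − 3.5 = 20.1 up to 30.5 − 2.6 = 27.9 months. The text does not give R.

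**3. What is done with the data.** Section 12.3.5 gives a summary by arm and Bayley version. Elsewhere in Sections 12.3.4 and 12.3.5 the protocol names a test or model where it wants one (CMH, Mann-Whitney, Fisher, MMRM). It names none for the 24-month data.

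**4. Effect of a scoring shift.** If examiners add on average b_L points in the LISA arm and b_C in the conventional arm, then

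observed difference = true difference + (b_L − b_C).

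The last term does not shrink as more children are seen. Splitting by Bayley version leaves it within each version.

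**5. Scale only.** The protocol has no figure to reproduce here. It gives no SD, alpha, power or effect size; the split 100 + 50 = 150 at 2:1 is consistent. For orientation, take an assumed composite-score SD of 12 to 18 and 60% to 100% of children assessed:

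half-width = 1.96 × SD × √(1/n_L + 1/n_C)

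| SD | LISA v conventional | Half-width (points) |
|---|---|---|
| 12 | 100 v 50 | 1.96 × 12 × 0.1732 = 4.07 |
| 15 | 100 v 50 | 1.96 × 15 × 0.1732 = 5.09 |
| 18 | 60 v 30 | 1.96 × 18 × 0.2236 = 7.89 |

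A hypothetical net shift of 2 to 5 points is mostly smaller than this random error, so it would be hard to detect in the data. The protocol plans no such interval, and the calculation pools the two Bayley versions that it keeps apart. The table shows order of magnitude and nothing more.

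**The case against.** The strongest reply is that no formal developmental comparison is planned. The study is called explorative, its sample-size section speaks of describing a profile, and the 24-month results go into an addendum. This stands as a limit on the point. A reader might infer a raised risk of a false-positive finding, but there is no planned test to be false, and error rates for one would describe an analysis that does not exist. It does not remove the point. Figures shown by arm will be compared, Section 2.1 frames the aim as LISA compared with conventional administration, and a biased descriptive difference is as wrong as a biased tested one.

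Three further inferences go beyond the text.
- A reader might infer that the examiner does know the arm, or that the team that treated the child does the examination. The protocol is silent on the first, and on the second says only that visits are at participating centers. What is established is that unmasked scoring is allowed.
- A reader might infer that every visit follows the main-phase results. Section 11 fixes the order of the locks, not of the visits; early-enrolled children may be seen first.
- A reader might infer that publication before the visits is planned. Section 24 says that the sponsor "is entitled to publish and/or present any results of this study at scientific meetings". That is permission without a date. The firmer route is the Section 22 summary to investigators, and even that has no stated date relative to the visits.

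Finally, an examiner who does not know the arm cannot apply published results to a child. That is correct, and it means that one masking rule deals with both routes.

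**Conclusion.** The point holds as a cheap improvement. The protocol as written allows the judgement-based 24-month items to be scored by someone who knows the arm and who, for later-enrolled children, may also have seen a summary of the main-phase report. The consequence is possible bias in a descriptive contrast between arms.

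The size of that bias cannot be estimated from the document. It would be the net difference in scoring between arms, and it requires a lean in the same direction across approximately 25 sites. The conclusion rests on two things: the protocol's silence on masking, and the fact that these items need examiner judgement. It does not depend on the assumed SD, follow-up or shifts.

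**What to change.** Add to Sections 7.1.9 and 7.2.4 that the person who administers the Bayley scales and completes the cerebral palsy, communication and respiratory items did not perform or assist that child's surfactant procedure and is not shown the treatment arm. Ask parents not to disclose the arm at the visit. Add one eCRF item recording whether the examiner knew the arm, so that the extent of unmasking can be reported beside the summaries.

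The cost is protocol wording and one eCRF field. No additional assessor is needed, because the arm is withheld from the person who already does the visit. Treatment, sample size and planned summaries are unchanged. The downsides are a small constraint on whom a site may assign to the visit, and some unmasking by parents, which the eCRF item records but does not prevent.

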APPENDIX III**COMPLICATIONS OF PREMATURITY**

- **Air leaks** (pneumothorax, pneumomediastinum, pneumopericardium, pneumoperitoneum)
- **Apnea of prematurity**
- **Focal intestinal perforation (Neonatal spontaneous intestinal perforation)**
- **Germinal matrix hemorrhage/Intraventricular hemorrhage:** to be classified according to the following [28,29]:
 - Grade I - Germinal matrix hemorrhage only or germinal matrix hemorrhage plus intraventricular hemorrhage less than 10% of ventricular area.
 - Grade II – Germinal matrix hemorrhage and intraventricular hemorrhage; 10 to 50% of ventricular area.
 - Grade III - Germinal matrix hemorrhage and intraventricular hemorrhage involving more than 50% of ventricular area; lateral ventricles are usually distended.
 - Grade IV: Hemorrhagic infarction in periventricular white matter ipsilateral to intraventricular hemorrhage (also called periventricular hemorrhagic infarction).
- **Necrotizing enterocolitis**, to be classified according to modified Bell staging criteria [30,31]
- **Patent ductus arteriosus**
- **Periventricular leukomalacia**
- **Pulmonary hemorrhage**
- **Pulmonary interstitial emphysema**
- **Retinopathy of prematurity** – classification related to stage, localization and extent according to “The International Classification of Retinopathy of Prematurity Revisited” [32,33]

